10.3 Responsibilities of the investigator and IRB/IEC

Before initiating a trial, the investigator/institution must obtain approval/favorable opinion from the Institutional Review Board/Independent Ethics Committee (IRB/IEC) for the trial protocol, written informed consent form, consent form updates, patient recruitment procedures (e.g., advertisements) and any other written information to be provided to patients. Prior to study start, the investigator is required to sign a protocol signature page confirming his/her agreement to conduct the study in accordance with these documents and all of the instructions and procedures found in this protocol and to give access to all relevant data and records to Novartis monitors, auditors, Novartis Quality Assurance representatives, designated agents of Novartis, IRBs/IECs, and regulatory authorities as required. If an inspection of the clinical site is requested by a regulatory authority, the investigator must inform Novartis immediately that this request has been made.

10.4 Publication of study protocol and results

The key design elements of this protocol will be posted in a publicly accessible database such as clinicaltrials.gov. In addition, upon study completion and finalization of the study report the results of this trial will be either submitted for publication and/or posted in a publicly accessible database of clinical trial results.

10.5 Quality Control and Quality Assurance

Novartis maintains a robust Quality Management (QM) system that includes all activities involved in quality assurance and quality control, including the assignment of roles and responsibilities, the reporting of results, and the documentation of actions and escalation of issues identified during the review of quality metrics, incidents, audits and inspections.

Audits of investigator sites, vendors, and Novartis systems are performed by Novartis Pharma Auditing and Compliance Quality Assurance (CQA), a group independent from those involved in conducting, monitoring or performing quality control of the clinical trial. The clinical audit process uses a knowledge/risk based approach.

Audits are conducted to assess GCP compliance with global and local regulatory requirements, protocols and internal SOPs, and are performed according to written Novartis processes.

11 Protocol adherence

This protocol defines the study objectives, the study procedures and the data to be collected on study participants. Additional assessments required to ensure safety of patients should be administered as deemed necessary on a case by case basis. Under no circumstances is an investigator allowed to collect additional data or conduct any additional procedures for any research related purpose involving any investigational drugs under the protocol.

Investigators ascertain they will apply due diligence to avoid protocol deviations. If an investigator feels a protocol deviation would improve the conduct of the study this must be considered a protocol amendment, and unless such an amendment is agreed upon by Novartis and approved by the IRB/IEC and health authorities, where required, it cannot be implemented.

Appendix 1: Clinically notable laboratory values

Only selected lab parameters which have potential to be sensitive to erenumab exposure are listed.

Notable Values			
Laboratory Variable	Gender (M/F/Both)	Standard Units	SI Units
LIVER FUNCTION AND RELATED VARIABLES			
SGOT (AST)	F	>93 U/L	>93 U/L
SGOT (AST)	M	>111 U/L	>111 U/L
SGPT (ALT)	F	>90 U/L	>90 U/L
SGPT (ALT)	M	>123 U/L	>123 U/L
Total bilirubin	Both	>3.6 mg/dL	>63 µmol/L
Alkaline Phosphatase	F	>832 U/L	>832 U/L
Alkaline Phosphatase	M	>1032 U/L	>1032 U/L
HEMATOLOGY VARIABLES			
Neutrophils	Both	<1.5x 10 ³ /uL	<1.5x10 ⁹ /L

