Women are considered post-menopausal and not of child bearing potential if they have had 12 months of natural (spontaneous) amenorrhea with an appropriate clinical profile (e.g. age appropriate, history of vasomotor symptoms) or have had surgical bilateral oophorectomy (with or without hysterectomy), total hysterectomy or tubal ligation at least 6 weeks ago. In the case of oophorectomy alone, only when the reproductive status of the woman has been confirmed by follow up hormone level assessment is she considered not of child bearing potential.

20. Use of other investigational drugs within 5 half-lives of enrollment, or until the expected pharmacodynamic effect has returned to baseline, whichever is longer.
21. History of hypersensitivity to the study drug or its excipients (including topiramate) or latex.
22. Patients not suitable for treatment with topiramate according to topiramate SmpC. Conditions listed under 4.4 Warnings and precautions in topiramate SmPC (e.g., risk of/history of nephrolithiasis, decreased renal function, risk of/history of eye disorders, risk of/history of metabolic acidosis) could be deemed as exclusion criterion at discretion of the investigator.
23. Any prior exposure to (investigational) prophylactic migraine products targeting the CGRP pathway, including previous erenumab studies.
24. Unlikely to be able to complete all protocol required study visits or procedures, and/or to comply with all required study procedures (e.g., independent completion of electronic diary items) to the best of the patient's and investigator's knowledge
25. Patients who may be dependent on the sponsor or investigator
26. Patient has not been committed to an institution by virtue of an order issued either by the judicial or the administrative authorities,

5 Treatment

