6.5 Safety

Safety assessments will include:

- Treatment discontinuations due to AEs
- Adverse events (Section 7.1)
- Physical examination
- Vital signs
- ECG
- Height/weight
- Laboratory evaluations
- Pregnancy testing (females of childbearing potential)
- Columbia Suicide Severity Rating Scale (C-SSRS) (Section 7.6)

The timing and frequency of these assessments are outlined in Table 6-1 and Table 6-2.

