6.5.4.2 Clinical chemistry

Bilirubin (total, direct and indirect), alkaline phosphatase, AST (SGOT), ALT (SGPT), GGT, creatinine and estimated creatinine clearance (GFR) will be measured. Clinical chemistry assessment will be performed at Screening (Visit 0), begin of DBTE (Visit 101), during DBTE two weeks after topiramate titration phase (Visit 108), at the end of DBTE (Visit 199) and at follow up (Visit 201).

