7.1 Adverse events

An adverse event (AE) is any untoward medical occurrence (e.g., any unfavorable and unintended sign [including abnormal laboratory findings], symptom or disease) in a patient or clinical investigation patient from randomization (Visit 101) until the end of study visit (16 weeks after the last IMP injection). Any events occurring during the Screening and Baseline Epochs and conditions that were already present at the time of informed consent should be documented as medical history. An AE may or may not be temporally or causally associated with the use of a medicinal (investigational) product.

In addition, all reports of intentional misuse and abuse of the product are also considered an adverse event irrespective if a clinical event has occurred.

The occurrence of adverse events must be sought by non-directive questioning of the patient at each visit during the study. Adverse events also may be detected when they are volunteered by the patient during or between visits or through physical examination findings, laboratory test findings, or other assessments.

Abnormal laboratory values or test results constitute adverse events only if they fulfill at least one of the following criteria:

- they induce clinical signs or symptoms,
- they are considered clinically significant,
- they require therapy.

Clinically significant abnormal laboratory values or test results must be identified through a review of values outside of normal ranges/clinically notable ranges, significant changes from baseline or the previous visit, or values which are considered to be non-typical in patient with underlying disease. Investigators have the responsibility for managing the safety of individual patient and identifying adverse events. Alert ranges for laboratory and other test abnormalities are included in Appendix 1.

Adverse events must be recorded in the Adverse Events eCRF under the signs, symptoms or diagnosis associated with them, accompanied by the following information:

- the severity grade
 - mild: usually transient in nature and generally not interfering with normal activities
 - moderate: sufficiently discomforting to interfere with normal activities
 - severe: prevents normal activities
- its relationship to the study treatment
 - Yes
 - No

- its duration (start and end dates) or if the event is ongoing an outcome of not recovered/not resolved must be reported.

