### **2.8.3 Laboratory data**

Summary statistics of laboratory hematology- and blood chemistry results will be presented as absolute value as well as change from baseline by visit, treatment and laboratory test category. Change from baseline will be summarized for each time point and only for patients with both baseline and post-baseline assessment.

Clinically notable laboratory values will be flagged and listed by treatment group.

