**Table 2.8.1.1-1. Clinically notable laboratory values**

Notable values			
Laboratory variable	Gender (M/F/Both)	Standard Units	SI Units
Liver function and related variables			
SGOT (AST)	F	> 93 U/L	> 93 U/L
SGOT (AST)	M	> 111 U/L	> 111 U/L
SGPT (ALT)	F	> 90 U/L	> 90 U/L
SGPT (ALT)	M	> 123 U/L	> 123 U/L
Total bilirubin	Both	> 3.6 mg/dL	> 63 µmol/L
Alkaline Phosphatase	F	> 832 U/L	> 832 U/L
Alkaline Phosphatase	M	> 1032 U/L	> 1032 U/L
Hematology variables			
Neutrophils	Both	< 1.5 x 10  /µL	< 1.5 x 10  /L

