### 2.8.4.2 Vital signs

Assessed vital signs include:

- systolic/diastolic blood pressure
- pulse rate
- temperature

Patient's values on blood pressure and pulse rate will be calculated as a mean of three readings. Readings with missing values will be ignored.

Descriptive summary statistics presented by type of measurement and treatment group will contain vital signs measurements for each study visit as well as change from baseline.

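### Collected safety data are under-analysed: the SAP has no post-baseline summary of body weight and drops the protocol's maximum-change analysis, leaving renal values without a patient-level summary of extremes

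*Protocol*

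**What the plan says.** **Laboratory flags.** Protocol Appendix 1 introduces its table with the sentence "Only selected lab parameters which have potential to be sensitive to erenumab exposure are listed". The table holds AST, ALT, total bilirubin, alkaline phosphatase and neutrophils. The SAP repeats the same five under "Table 2.8.1.1-1. Clinically notable laboratory values", and SAP 2.8.3 uses them as follows: "Clinically notable laboratory values will be flagged and listed by treatment group". Protocol 7.1 also sends investigators to this list: "Alert ranges for laboratory and other test abnormalities are included in Appendix 1".

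**Laboratory summaries.** Protocol 6.5.4.2 names the chemistry panel, including renal function: "creatinine and estimated creatinine clearance (GFR) will be measured". SAP 2.8.3 gives all haematology and chemistry results summary statistics, as values and as changes from baseline, by visit and treatment. Protocol 9.5.1.2 plans these summaries too and adds an analysis of the largest change from baseline, parameter by parameter, within each study period. SAP 2.8.3 does not contain that addition.

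**Weight.** Protocol 6.5 lists "Height/weight" among the safety assessments, and 6.5.3 says how weight is measured. Table 6-2 schedules it, as data for the clinical database, at V199-ASA and V201-ASA. In the SAP, weight appears in 2.3.2 as a demographic variable. The list in SAP 2.8.4.2 that opens "Assessed vital signs include" holds blood pressure, pulse rate and temperature only.

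**The concern.** Protocol 1.2 sets out to compare the safety of two active drugs and says the data will support health technology assessments and reimbursement negotiations. For that use the safety report should summarise what was measured in both arms.

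Two omissions stand out. A measurement taken for safety has no planned post-baseline output. And the one laboratory display that works at patient level covers parameters picked with one of the two drugs in mind, while the planned analysis that would have covered all parameters has gone. At stake is the completeness of the descriptive safety tables, not a test or an error rate.

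**Working it through.** No formula in the plan is at issue, so the check sets what is collected beside what is analysed.

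| Data collected | By-visit summary by arm (SAP 2.8) | Patient-level flag (SAP 2.8.3) |
|---|---|---|
| AST, ALT, total bilirubin, alkaline phosphatase | yes | yes |
| Direct and indirect bilirubin, GGT | yes | no |
| Creatinine, estimated clearance | yes | no |
| Neutrophils (part of the differential) | yes | yes |
| Other haematology in protocol 6.5.4.1 | yes | no |
| Body weight | no | no |

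**Counts.** Protocol 6.5.4.2 names 3 bilirubin fractions plus alkaline phosphatase, AST, ALT, GGT, creatinine and clearance: 3 + 6 = 9 chemistry items. Flagged: 4 of 9, all hepatic. Renal items flagged: 0 of 2. Renal items with by-visit summaries: 2 of 2. The flag list is 4 hepatic + 1 haematology = 5 variables.

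**What the dropped analysis would have covered.** The maximum-change analysis in protocol 9.5.1.2 applies to every parameter, so it would have included creatinine and clearance. Chemistry is scheduled at Visits 0, 101, 108, 199 and 201. The first two are at or before the start of treatment, which leaves 5 − 2 = 3 post-baseline samples: two in the double-blind epoch and one at follow-up. A footnote to Table 6-2 allows further chemistry and haematology samples when adverse events call for them. A worst-value summary can take in those extra samples; a table built on scheduled visits shows them poorly.

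**What the by-visit tables can show.** One patient whose value changes by d moves the arm's mean change by d/n. With the SAP's roughly 375 per arm this is d/375, or 0.27% of d; with the protocol's 700 patients split 1:1 it is d/350, or 0.29% of d. The general rules in SAP 2.1 also call for the minimum and maximum, so the single most extreme value in each direction at each visit would be visible. What stays hidden is how many patients had a marked change and what each patient's own worst value was.

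**Whether weight is covered elsewhere.** Protocol 6.5.2 and SAP 2.8.4.2 both define vital signs without weight. SAP 2.1.1.5 names laboratory, vital signs, ECG and C-SSRS as the visit-based safety data, again without weight. Protocol 9.5.1 covers adverse events, laboratory data and vital signs only. Number of post-baseline weight summaries planned: 0.

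**The case against.** - **Renal function is analysed.** A reader might infer that creatinine and clearance have no planned analysis. They do: values and changes from baseline, by visit and arm, with minimum and maximum. This stands, and it narrows the point to the missing patient-level summary.
- **The thresholds are even-handed.** A reader might infer that the two drugs are judged on unequal terms. They are not: each of the five criteria applies to every patient, and a topiramate patient with a raised ALT is flagged as an erenumab patient would be. Why a parameter was chosen does not limit whose abnormal value it detects. Appendix 1 also states its own restriction openly.
- **No comparator effect is shown.** Exclusion criterion 22 mentions "decreased renal function, risk of/history of eye disorders, risk of/history of metabolic acidosis". It is tempting to read this as evidence that topiramate impairs renal function. The criterion lists label precautions that may make a patient unsuitable; it does not say that the drug causes renal decline, and the label itself is not among the documents. Nor do the documents name weight change as a topiramate effect: protocol 3.6 lists paraesthesia, fatigue, memory and cognitive disturbance, and mood problems. The weight point rests only on data being collected for safety and not summarised.
- **Harms have other routes.** Protocol 7.1 requires review of values outside normal ranges and of significant changes from baseline, and clinically significant ones become adverse events. SAP 2.8.1 tabulates adverse events by arm, and AE-related discontinuation is the primary endpoint. This stands.
- **More may exist out of sight.** SAP 2.1 refers to table shells that are not in the file, and part of the SAP before its appendix is redacted. Either could hold a weight table or explain the dropped analysis. The visible text of SAP 2.8.3 and 2.8.4 shows no redaction where such outputs would sit.

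None of this supplies a post-baseline weight summary or accounts for the missing maximum-change analysis.

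**Conclusion.** Two descriptive omissions stand. Body weight has no planned summary after baseline. And the maximum-change analysis in protocol 9.5.1.2 is absent from SAP 2.8.3, so the only patient-level laboratory display covers five variables selected for sensitivity to erenumab, and neither renal item has one.

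The importance is low: a useful improvement, not a defect in the trial's inference. The primary test does not depend on it. If the gap hides anything on the topiramate side it would under-display the comparator's effects, so it gives the erenumab tolerability claim no advantage. The documents do not support the broader reading that topiramate's harms go unreported or that the arms are treated unequally.

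The conclusion assumes that the visible SAP text is the full commitment for these outputs.

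**What to change.** 1. **SAP 2.8.4:** add body weight and its change from baseline, by visit and arm.
2. **SAP 2.8.3:** restore the protocol's maximum-change analysis for all measured haematology and chemistry parameters, including creatinine and estimated clearance, and state the direction of interest for each parameter. A shift table of baseline against worst post-baseline value, using the central laboratory's normal range, would serve equally well and needs no new notable thresholds. If the analysis was dropped on purpose, say so and give the reason.
3. **SAP 2.8.3 and its notable-value table:** label the listing as limited to parameters considered sensitive to erenumab, so that an empty column is not taken as a finding about laboratory safety in general.

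The cost is SAP wording and a few descriptive tables from data already collected. No new assessments and no statistical tests are needed.

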Appendix 2: Liver event and Laboratory trigger Definitions and Follow-up Requirements

Table 13-1 Liver Event and Laboratory Trigger Definitions

	Definition/ threshold
LIVER LABORATORY TRIGGERS	
 • $3 \times \text{ULN} < \text{ALT/AST} \leq 5 \times \text{ULN}$ • $1.5 \times \text{ULN} < \text{TBL} \leq 2 \times \text{ULN}$
LIVER EVENTS	
 • $\text{ALT or AST} > 5 \times \text{ULN}$ • $\text{ALP} > 2 \times \text{ULN}$ (in the absence of known bone pathology) • $\text{TBL} > 2 \times \text{ULN}$ (in the absence of known Gilbert syndrome) • $\text{ALT or AST} > 3 \times \text{ULN}$ and $\text{INR} > 1.5$ • Potential Hy's Law cases (defined as $\text{ALT or AST} > 3 \times \text{ULN}$ and $\text{TBL} > 2 \times \text{ULN}$ [mainly conjugated fraction] without notable increase in ALP to $> 2 \times \text{ULN}$) • Any clinical event of jaundice (or equivalent term) • $\text{ALT or AST} > 3 \times \text{ULN}$ accompanied by (general) malaise, fatigue, abdominal pain, nausea, or vomiting, or rash with eosinophilia • Any adverse event potentially indicative of a liver toxicity*

*These events cover the following: hepatic failure, fibrosis and cirrhosis, and other liver damage-related conditions; the non-infectious hepatitis; the benign, malignant and unspecified liver neoplasms

Table 13-2 Follow Up Requirements for Liver Events and Laboratory Triggers

Criteria	Actions required	Follow-up monitoring
Potential Hy's Law case ^a	
 • Discontinue the study treatment immediately • Hospitalize, if clinically appropriate • Establish causality • Complete liver CRF 	ALT, AST, TBL, Alb, PT/INR, ALP and γ GT until resolution ^c (frequency at investigator discretion)
ALT or AST		
$> 8 \times \text{ULN}$	
 • Discontinue the study treatment immediately • Hospitalize if clinically appropriate • Establish causality • Complete liver CRF 	ALT, AST, TBL, Alb, PT/INR, ALP and γ GT until resolution ^c (frequency at investigator discretion)
$> 3 \times \text{ULN}$ and $\text{INR} > 1.5$	
 • Discontinue the study treatment immediately • Hospitalize, if clinically appropriate • Establish causality • Complete liver CRF 	ALT, AST, TBL, Alb, PT/INR, ALP and γ GT until resolution ^c (frequency at investigator discretion)
> 5 to $\leq 8 \times \text{ULN}$	
 • Repeat LFT within 48 hours • If elevation persists, continue follow-up monitoring • If elevation persists for more than 2 weeks, discontinue the study drug • Establish causality 	ALT, AST, TBL, Alb, PT/INR, ALP and γ GT until resolution ^c (frequency at investigator discretion)

Criteria	Actions required	Follow-up monitoring
	
 Complete liver CRF 	
> 3 × ULN accompanied by symptoms ^b	
 Discontinue the study treatment immediately Hospitalize if clinically appropriate Establish causality Complete liver CRF 	ALT, AST, TBL, Alb, PT/INR, ALP and γGT until resolution ^c (frequency at investigator discretion)
> 3 to ≤ 5 × ULN (patient is asymptomatic)	
 Repeat LFT within the next week If elevation is confirmed, initiate close observation of the patient 	Investigator discretion Monitor LFT within 1 to 4 weeks
ALP (isolated)		
> 2 × ULN (in the absence of known bone pathology)	
 Repeat LFT within 48 hours If elevation persists, establish causality Complete liver CRF 	Investigator discretion Monitor LFT within 1 to 4 weeks or at next visit
TBL (isolated)		
> 2 × ULN (in the absence of known Gilbert syndrome)	
 Repeat LFT within 48 hours If elevation persists, discontinue the study drug immediately Hospitalize if clinically appropriate Establish causality Complete liver CRF 	ALT, AST, TBL, Alb, PT/INR, ALP and γGT until resolution ^c (frequency at investigator discretion) Test for hemolysis (e.g., reticulocytes, haptoglobin, unconjugated [indirect] bilirubin)
> 1.5 to ≤ 2 × ULN (patient is asymptomatic)	
 Repeat LFT within the next week If elevation is confirmed, initiate close observation of the patient 	Investigator discretion Monitor LFT within 1 to 4 weeks or at next visit
Jaundice	
 Discontinue the study treatment immediately Hospitalize the patient Establish causality Complete liver CRF 	ALT, AST, TBL, Alb, PT/INR, ALP and γGT until resolution ^c (frequency at investigator discretion)
Any AE potentially indicative of a liver toxicity*	
 Consider study treatment interruption or discontinuation Hospitalization if clinically appropriate Establish causality Complete liver CRF 	Investigator discretion

^aElevated ALT/AST > 3 × ULN and TBL > 2 × ULN but without notable increase in ALP to > 2 × ULN

^b(General) malaise, fatigue, abdominal pain, nausea, or vomiting, or rash with eosinophilia

^cResolution is defined as an outcome of one of the following: (1) return to baseline values, (2) stable values at three subsequent monitoring visits at least 2 weeks apart, (3) remain at elevated level after a maximum of 6 months, (4) liver transplantation, and (5) death.

## List of abbreviations

AE	Adverse event
ASA	Abbreviated schedule of assessments
ATC	Anatomic Therapeutic Chemical classification
CRO	Contact Research Organisation
DBTE	Double-Blind Treatment Epoch
ECG	Electroencephalography
eCRF	electronic Case Report Form
EoS	End of the Study
FAS	Full Analysis Set
HRQoL	Health Related Quality of Life
IMP	investigational medicinal product
IRT	Interactive Response Technology
LPLV	last patient last visit
MCS	Mental Component Summary
MedDRA	Medical Dictionary for Drug Regulatory Affairs
MMD	Monthly Migraine Days
ODS	Output Delivery System
PCS	Mental Component Summary
PRO	Patient Reported Outcome
PT	Preferred Term
RAS	Randomized Analysis Set
SAE	Serious Adverse Event
SAF	Safety Analysis Set
SAP	statistical analysis plan
SmPC	Summary of Product Characteristics
SOC	System Organ Class
TEAE	Treatment-Emergent Adverse Event
TFLs	Tables, Figures, Listings
WHO	World Health Organization

